**Assessment and Augmentation of Lip Appearance in Specific Study
Populations**

NCT04839692

December 29, 2021

Assessment and Augmentation of Lip Appearance in Specific Study Populations

PRINCIPAL INVESTIGATORS:

[name], PhD
Cutaneous Biology Research Center (CBRC)
Massachusetts General Hospital Research Institute
[name]
[contact]
[contact]
e-mail: [contact]

CO- PRINCIPAL INVESTIGATOR:

[name], MSHS
Cutaneous Biology Research Center (CBRC)
Massachusetts General Hospital Research Institute
[name]
[contact]
[contact]
e-mail: [contact]

VERSION DATE

December 29,2021

TABLE OF CONTENTS

	Page
I. OBJECTIVE	3
II. BACKGROUND	3
III. AIMS	4
IV. SUBJECT SELECTION	
a. Inclusion Criteria	4
b. Exclusion Criteria	4
c. Source and recruitment of subjects	5
V. SUBJECT ENROLLMENT	
a. Method of enrollment	6
b. Informed consent form (ICF)	6
VI. STUDY PROCEDURES	6
a. Study visits and procedures	6
b. Drugs to be used	9
c. Devices to be used	9
d. Procedures/Interventions	10
e. Data to be collected and when data is collected	11
f. Remuneration	11
VII. BIOSTATISTICAL ANALYSIS	11
VIII. RISKS AND DISCOMFORTS	14
IX. POTENTIAL BENEFITS	
a. Potential benefits to subjects	15
b. Potential benefits to society.....	15
X. MONITORING AND QUALITY ASSURANCE	
a. Independent monitoring of source data	15
b. Safety monitoring	15
c. Outcome monitoring	16
d. Adverse Event reporting.....	16
XII. Data Management	
a. Data collection	17
b. Record retention	17
XIII. IRB Review and Approval	17
XIV. References	18
Appendix A (Study Schema)	19

I. OBJECTIVES

The objectives of this study are:

- To determine the effects of aging on the lips and perioral area by comparing quantitative changes in lip; and
- To validate the role of optical coherence tomography (OCT) in investigating lip microcirculation; and
- To evaluate any volume, color and texture change of the lips pre and post treatment
- To investigate pain levels from lip filler treatment

To achieve the objectives, the study aims to obtain data from two specific study populations, including:

- 1) Aged females, otherwise healthy (≥ 60 years);
- 2) Young females, otherwise healthy (21-30 years)

II. BACKGROUND

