Skin aging is a complex biological process mainly influenced by two independent mechanisms, intrinsic and extrinsic skin aging [1]. Intrinsic skin aging is determined primarily by inherent genetic factors, hormonal status, cellular metabolism and function [2]. It represents degenerative aging processes seen in other organ systems as a consequence of the passage of time. Extrinsic skin aging results from various external influences including solar UV radiation, health and lifestyle factors, such as tobacco smoking, environmental pollution, and other systemic conditions, such as diabetes and renal insufficiency [3-5].

In skin with chronic exposure to UV radiation, termed photoaging, alterations in skin structure and function depend primarily on the degree of sun exposure and baseline skin pigment. UV radiation induces collagen breakdown. Diminution of collagen framework that supports vascular plexus within the skin leads to broken vessels [8]. The Langerhans cell population representing immune system of the skin is found to be reduced after chronic exposure to UV radiation contributing to impaired immune response to antigen and skin cancer cells [6,7].

These age-related changes caused by chronic sun exposure have not been well-documented in the lips [10]. The majority of literature on the aging lip has focused on volume loss. Hyaluronic-acid based fillers have been used primarily for volume augmentation, but their effect on lip color and texture has seldom been defined [9,12].

We propose to study aging of the cutaneous changes of human skin anatomy in the lips and perioral area to better understand and quantify the aging process in this, including the effect of age on lip redness.

We also aim to test the effects of a common lip augmentation procedure, hyaluronic-acid based fillers, on the appearance of aging lips, in addition to the tolerability of this procedure. We hypothesize that dermal lip fillers may decrease the redness of the lips.

Besides, we want to evaluate oxytocin level changes and relate it to subjects' satisfaction with procedure.

The study will take place at MGH's Clinical Unit for Research Trials & Outcomes in Skin (CURTIS) at [name] or Translational Clinical Research Center (TCRC) on the 12th floor of the White Building.

III. Specific AIMS

To:

- Compare the changes in skin anatomy due to intrinsic aging
- Correlate clinical assessment with OCT imaging;

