- Compare changes in lip color, texture and volume before and after filler with non-invasive imaging, including digital photography, OCT and three-dimensional imaging
- To assess the tolerability of lip filler by evaluating pain level from lip filler treatment at initial insertion and overall procedural pain
- To evaluate how oxytocin levels change during and after an aesthetic procedure.
- To assess lip color change after the procedure.
- To evaluate patient satisfaction related to the procedure.

IV. SUBJECT SELECTION

Subjects will be screened to determine if they meet all the eligibility criteria specified below. We will recruit and screen up to 50 subjects with the goal of 40 subjects enroll and complete the study (20 per study arm).

a. Inclusion Criteria

1. Subjects must be able and willing to provide written informed consent and comply with the requirements of the study protocol;
2. In good general health, based on answers provided during the screening visit;
3. Subjects must be able to read and understand English;
4. Female subjects;
5. Aged 21-30 years and Post menopausal women;
6. Skin Types (Fitzpatrick Skin Phototypes I-VI);

* Smoking history is self-report.

7. Have very thin to moderately thick lips (Lip Fullness Grading Scale [LFGS] scores 0–2).

b. Exclusion Criteria

1. Participation in another investigational drug or device clinical trial in the past 30 days;
2. Are pregnant or lactating;
3. Intake of hormone replacement therapy (HRT) in the past 6 months;
4. Have a history of drug or alcohol abuse or have reported habitual alcohol intake greater than 2 standard drinks per day [e.g., 2 beers, 2 glasses of wine, or 2 mixed drinks];
5. Presence of eczema, psoriasis, or any other skin disease on the lips or perioral skin;
6. Have birth marks, tattoos, scars, or any other disfiguration of the skin in the skin area of interest;
7. Use of any anti-aging skin care products containing retinoic acid, retinol, or other retinoids (e.g. tazarotene, adapalene) or estrogen on the skin area of interest in the past 6 months;
8. Use of any prescription topical medication, such as corticosteroids or hydroquinone on the skin area of interest in the past 6 months;
9. Have a history of photodynamic therapy treatment or any skin rejuvenation procedure on the skin area of interest;
10. History of blood-clotting abnormality;
11. History of keloid formation or hypertrophic scarring;

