All video recording data files will be labeled with the study subject number assigned to each subject upon consent. No identifying information will be used in labeling the video data files and the files will be stored on Partners Dropbox. The videos will be stored at Partners Dropbox until 7 years after the end of this study when all the copies will be permanently deleted from this drive.

Only study staff will have access to the videos (for storage purposes- like research coordinators or for assessment - investigators) unless the subject authorizes, by signalizing it in the consent form, the use of their video recordings for the following purposes:

- medical or pharmaceutical publications, or presentations in conferences
- educating health care professionals (such as physicians and nurses) through electronic materials (iPads), brochures and the healthcare professional website
- patient-focused websites and patient-handouts / industry ads

If the subject agrees (in the consent form) with the use of her video recording for the purposes cited above the video will be shared with pharmaceutical companies (ex. Galderma- Lip filler producer) or will be shared with other doctors during lectures in medical conferences.

Oxytoxin

The Brigham Research Core lab will process the ELISA assay to evaluate oxytocin levels per the Oxytocin EIA kit which is a colorimetric competitive enzyme immunoassay kit, with very low reactivity with vasopressin.

c. Statistical Methods

The study is intended to gather empirical data about the volume, color, texture and microcirculation change in the lips and perioral area; and pain assessment of treatment. Descriptive statistics will be collected to present quantitative descriptions of changes in lips and perioral area from pretreatment compared to post-treatment.

VIII. RISKS AND DISCOMFORTS

a. Complications of surgical and non-surgical procedures

Subjects might encounter an experience of discomfort during OCT imaging procedure due to the application of pressure to occlude blood vessels in the skin. There will be no harm caused by vessel occlusion and study staff will explain the procedure to subjects prior to taking the OCT images. There are no known adverse effects of the three-dimensional imaging system (Cherry) other than psychological distress from seeing a high-resolution photo that may highlight imperfections. This is no different than routine professional photography.

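### Section VII.c plans only before-and-after description, so the effect of age on lip redness has no young-versus-older analysis; separately, an unadjusted cohort contrast cannot support the intrinsic-aging label used for anatomy and microvasculature

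*Combined protocol and SAP*

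**What the plan says.** **The age question.** The first objective (Section I) is "To determine the effects of aging on the lips and perioral area by comparing quantitative changes in lip", pursued in women aged 21-30 and women aged 60 or over. Section II narrows part of it to redness: "including the effect of age on lip redness". One aim in Section III goes further: "Compare the changes in skin anatomy due to intrinsic aging". Section IX.b also ties lip microvasculature to intrinsic aging.

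**The filler question.** Another aim in Section III is "Compare changes in lip color, texture and volume before and after filler with non-invasive imaging". Section II adds a hypothesis that filler may reduce redness.

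**The analysis.** Section VII.c states: "Descriptive statistics will be collected to present quantitative descriptions of changes in lips and perioral area from pretreatment compared to post-treatment". It mentions neither age nor cohort. Section VII.b says that OCT capillary metrics will serve comparisons between and within cohorts, but gives no summary measure, visit or model. Its Cherry Imaging paragraph lists redness, roughness and volume as things to analyse and does not mention cohorts.

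**What drives skin aging.** Section II separates intrinsic from extrinsic aging: "Extrinsic skin aging results from various external influences including solar UV radiation, health and lifestyle factors, such as tobacco smoking". For photoaged skin it says "alterations in skin structure and function depend primarily on the degree of sun exposure and baseline skin pigment".

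**Who enters and what is recorded.** Section IV.a admits all Fitzpatrick phototypes, does not exclude smokers, and describes smoking history as self-reported. Its criterion 5 defines the older group as postmenopausal, with no minimum age. Section VI.e gives a closed list of data. It includes medical history but does not name phototype, smoking or sun exposure.

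**The concern.** There are two separate gaps.

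First, the design is built on two age cohorts, but the methods text contains only a contrast over time. Followed as written, it describes what filler does and leaves the redness-by-age question either unanswered or answered by a comparison chosen after the data are seen.

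Second, where the protocol attributes differences to intrinsic aging, the cohorts cannot isolate it. They are defined by age, so they are not randomised, and no matching, stratification or adjustment is planned. An older-minus-young difference in anatomy or vessels mixes intrinsic aging with whatever differs between the cohorts in sun exposure, smoking and pigment. A larger sample would not remove that.

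The meaning of any cohort contrast also depends on whether the older group is 60 and over (Section I) or postmenopausal (Section IV.a).

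**Working it through.** **Is there a between-cohort analysis?**

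| Question | Where asked | Matching analysis |
|---|---|---|
| Effect of filler on colour, texture, volume | III | VII.c, before v after |
| Age and OCT vessel metrics | I, III, IX.b | VII.b, one sentence, no method |
| Age and redness | II, under the first objective in I | None |
| Age and roughness or volume | Only by implication from I | None |

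The explicit gap is redness.

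**Precision of the missing contrast.** Section IV aims for 40 completers, 20 per arm. It gives no alpha, power, SD or effect size, so there is no planned figure to reproduce. In SD units:

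- Older minus young, 95% half-width: t(38, 0.975) × √(2/20) = 2.024 × 0.316 = 0.64 SD.
- Change within one cohort: t(19, 0.975)/√20 = 2.093/4.472 = 0.47 SD of change. If only 16 are treated and return (assumption): 2.131/4 = 0.53.

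**Possible confounding (assumed inputs).** Bias = difference in prevalence × effect of the factor. The documents give neither input. Imbalances of 0 to 40 points with effects of 0.5 to 1.0 SD give 0 to 0.4 × 1.0 = 0.40 SD.

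**What adjustment would cost.** Assume a binary covariate present in 60% of one cohort and 20% of the other.

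- Within-cohort variance: (0.24 + 0.16)/2 = 0.20. Total variance: 0.40 × 0.60 = 0.24. R² with cohort: 0.04/0.24 = 0.167. Variance inflation: 1/(1 − 0.167) = 1.20.
- With two covariates fitted, the base half-width is t(36, 0.975) × √(2/20) = 0.641.
- If one covariate is imbalanced, half-width = 0.641 × √1.20 × √(1 − 0.20b²), where b is its effect in SD.
- If both are imbalanced in this way and independent within cohort, inflation is 1.40 and half-width = 0.641 × √1.40 × √(1 − 0.40b²).

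| Effect b of each imbalanced covariate | Bias from one covariate | Half-width, one imbalanced | Half-width, two imbalanced |
|---|---|---|---|
| 0 | 0 | 0.70 | 0.76 |
| 0.5 | 0.20 | 0.68 | 0.72 |
| 1.0 | 0.40 | 0.63 | 0.59 |

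The unadjusted half-width is 0.64. With one imbalanced covariate, break-even is at b ≈ 0.92, a bias of 0.4 × 0.92 ≈ 0.37 SD. Below that, adjustment widens the interval.

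**Can smoking be adjusted for?** Take fewer than 3 ever-smokers in either cohort of 20 as too sparse (a working threshold, not from the documents). With X ~ Bin(20, p) and equal prevalence p in both cohorts, the chance is 1 − (1 − P(X ≤ 2))².

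| Assumed p | One cohort | Either cohort |
|---|---|---|
| 5% | 92% | 99% |
| 10% | 68% | 90% |
| 20% | 21% | 37% |
| 30% | 4% | 7% |

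**The case against.** A descriptive plan suits a study of 40, and descriptive tables could be split by cohort without a word being changed. That is fair as to style: no hypothesis test is needed. But Section VII.c names the contrast it will describe, and that contrast is over time.

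Four stronger readings are tempting, and the documents do not support them.

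- *No between-cohort comparison appears anywhere.* Section VII.b does announce one for OCT metrics. It lacks a method and does not cover redness.
- *An unadjusted redness contrast would be invalid.* Intrinsic aging is attached to skin anatomy and microvasculature, never to redness. Section II treats skin aging as intrinsic plus extrinsic, so sun and smoking are part of the aging it describes. For redness, the plain cohort difference answers the question asked.
- *The choice of Visit 1 image is wide open.* Section VI.a has Cherry images both before and after the procedure, but Section VI.c describes them as taken before treatment and at the last visit, and Section VI.d places imaging before injection. The pre-injection image is the natural baseline; the analysis text need only say so.
- *Regression adjustment is required.* No passage points to an actual imbalance, every bias figure above is assumed, and adjustment usually costs precision. It is an option.

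It is also fair to object that phototype and smoking may not be on file as analysable data. Skin colour is asked at telephone prescreening (Section IV.c), and smoking might fall under medical history, but Section VI.e lists neither by name.

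**Conclusion.** The point holds in two parts. First, the stated question about age and redness has no matching analysis. The contrast could be estimated from images already planned, with a 95% half-width of 0.64 SD at 20 per cohort. Second, an unadjusted cohort difference cannot carry the attribution to intrinsic aging in Sections III and IX.b, by the distinction that Section II itself draws.

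The first part rests on the text alone. The half-width assumes 20 analysed per cohort and a common SD. The size of any confounding is unknown: 0 to 0.40 SD is a range under stated assumptions, not an estimate. This is a gap in specification and wording that should be closed before analysis; it does not make the data collection unsound.

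**What to change.** 1. Add to Section VII.c: *For Cherry lip redness and each OCT metric from the Visit 1 pre-injection images (roughness and volume as supporting measures), report the older-minus-young mean difference with 95% CI, including subjects who have Visit 1 imaging only. Report Visit 2 minus Visit 1 pre-injection change within each cohort with 95% CI.* Imaging-only subjects arise because Section VI.a makes filler optional for completely inverted lips.
2. Replace the attribution to intrinsic aging with *associated with chronological age group*, and state that sun exposure, pigment and smoking are not separated from age.
3. Enter phototype and self-reported smoking history as data fields, add them to Section VI.e, and tabulate them by cohort. An adjusted difference may be shown as a sensitivity analysis where numbers allow.
4. Reconcile the two definitions of the older cohort (Sections I and IV.a) before the contrast is run. Note that entry restricted to LFGS 0-2 truncates any baseline volume contrast.

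**Cost.** Items 1, 2 and 4 need wording and no new images. Item 3 may need two fields to be collected or formally recorded. If the adjusted analysis is shown, its half-width in the assumed examples is 0.63 to 0.70 SD with one imbalanced covariate and 0.59 to 0.76 SD with two, against 0.64 unadjusted. At 5-10% smoking prevalence, smoking would usually be too sparse to include. Item 2 leaves a narrower claim than intrinsic aging.

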Appendix A: Study Schema

	Screening	Visit 1	Follow-up Call	Visit 2
Study Visit	<30 days	Day 0	3-7 days after Visit 1	2 weeks after Visit 1
Informed Consent	X			
Inclusion/Exclusion	X	X		
History/Demographics	X			
Review side effects/check-in			X	
Investigator Assessments		X	X	X
Digital Photography		X		X
3D Cherry Imaging		X		X
OCT Imaging		X		X
Filler Treatment		X		
Questionnaires		X		X
LFGS	X	X		X
Con Meds/Adverse Events		X	X	X
Blood Draw		X
